**8. Biomarker Sample Collection in Different Countries**

Collection of biological samples for biomarker research is straightforward in most jurisdictions. Some countries have specific laws and regulations regarding collection, labeling, storage, export, and/or use of exploratory samples. In addition, some regulations distinguish between DNA and non-DNA samples or between samples used for diagnostic purposes and samples collected for scientific research. Processes for the collection, labeling, storage, export, and/or use of biomarker samples should always adhere to the laws and regulations of the country/region in which those samples are collected.

**9. Return of Research Results to Study Participants**

Policies for the return of biomarker research results to study participants who request them vary among pharmaceutical companies. There are many considerations that pharmaceutical companies weigh when determining their policy regarding the return of biomarker research results to study participants. These include:

- i) the conditions under which biomarker research results were generated (i.e., exploratory research laboratory versus accredited diagnostic laboratory)
- ii) whether the results will have an impact on the medical care of the participant or on a related person, if applicable
- iii) whether genetic counseling is recommended (for genetic results)
- iv) the ability to accurately link the result to the individual from whom the sample was collected
- v) international, national, and local guidelines, policies, legislation, and regulations regarding participants' rights to access data generated on them

6

Renegar *et al.*, 2008 and Article 29 Data Protection Working Party (an advisory committee to the European Commission on the European Data Protection Directive) have addressed these considerations in detail in relation to pharmacogenomic research data and provided a list of documents addressing the general issue of return of research results.

**10. Benefits and Risks Associated with Biomarker Research**

**Benefits**

While it may not always directly benefit the study participant who is providing the samples, biomarker research can improve overall understanding of disease and treatment of future patients receiving therapies developed from such research. Patients are now benefiting from retrospective biomarker research conducted on samples collected from clinical trials and stored for exploratory research. One example is the recent label update to the EGFR antibody drugs cetuximab (Erbitux®) and panitumumab (Vectibix®) which highlights the value of KRAS status as a predictive biomarker for treatment of metastatic colorectal cancer with this class of drug.

The humanitarian benefit of human research is recognized by the Nuremberg Code. Provided that the degree of risk does not exceed that determined by the humanitarian importance of the problem to be solved, research participants should not be denied the right to contribute to the greater common good.

**Risks**

Risks associated with biomarker research are primarily related to the physical aspects of obtaining the sample and to patient privacy concerns.

Physical risks associated with biomarker sample collection in clinical trials can be characterized in two ways:

- i) negligible additional risk when the biomarker sample is collected as part of a procedure conducted to support

**I-PWG**  
International Partnership for the Use of Genetic Information in Women's Health

other core trial objectives, and ii) some added risk where the sampling procedure would otherwise have not been performed as a core component of a trial. Risks are also determined by the invasiveness of the sample collection procedure.

Privacy risks are generally those associated with the inappropriate disclosure and misuse of data. Pharmaceutical companies have policies and procedures for confidentiality protection to minimize this risk for all data collected and generated in clinical trials. These may vary across companies, but are based on industry standards of confidentiality and privacy protection highlighted in the following section. Importantly, privacy risks inherent to biomarker data are no greater than other data collected in a clinical trial.

**11. Privacy, Confidentiality, and Patient Rights**

Maintaining the privacy of study participants and the confidentiality of information relating to them is of paramount concern to industry researchers, regulators, and patients. Good Clinical Practice (GCP), the standard adhered to in pharmaceutical clinical research, is a standard that

*... provides assurance that the data and reported results are credible and accurate, and that the rights, integrity, and confidentiality of trial subjects are protected*,

where confidentiality is defined as, *The prevention of disclosure, to other than authorized individuals, of a sponsor's proprietary information or of a subject's identity*.

This standard dictates that *the confidentiality of records that could identify subjects should be protected, respecting the privacy and confidentiality rules in accordance with applicable regulatory requirements*.

Exploratory biomarker research in pharmaceutical development is commonly conducted in research laboratories that are not accredited to perform diagnostic tests used for healthcare decision-making. Therefore, results from exploratory biomarker research usually are not appropriate for use in making decisions about a trial participant's health. In addition, exploratory research data should not be included as part of a participant's medical record accessible for use by insurance companies. Legislation and policies to protect individuals against discrimination based on genetic information continually evolve based on social, ethical, and legal considerations. Examples of such legislation include the Human Tissue Act 2004 (UK) and the Genetic Information Nondiscrimination Act (GINA) 2008 (USA).

**12. Where to Get More Information?**

Educational resources related to biomarker and pharmacogenomic research that caters to health care professionals, IRBs/IECs, scientists, and patients are continually being created and are publicly available. Links to many of these resources are available through the I-PWG website: [www.i-pwg.org](http://www.i-pwg.org).

**13. What is I-PWG?**

The Industry Pharmacogenomics Working Group (I-PWG) (formerly the Pharmacogenetics Working Group) is a voluntary association of pharmaceutical companies engaged in pharmacogenomic research. The Group's activities focus on non-competitive educational, informational, ethical, legal, and regulatory topics. The Group provides information and expert opinions on these topics and sponsors educational/informational programs to promote better understanding of pharmacogenomic and other biomarker research for key stakeholders. The I-PWG interacts with regulatory authori-

I-PWG  
INDUSTRY PHARMACOGENOMICS WORKING GROUP

ities and policy groups to ensure alignment. More information about the I-PWG is available at: [www.i-pwg.org](http://www.i-pwg.org).

**www.i-pwg.org**

MK-3475-013-09 Final Protocol

16-Apr-2020

Confidential

05GL8N

## 12.4 ECOG Performance Status

Grade	Description
0	Fully active, able to carry on all pre-disease performance without restriction
1	Restricted in physically strenuous activity but ambulatory and able to carry out work of a light or sedentary nature, e.g., light housework, office work
2	Ambulatory and capable of all self-care but unable to carry out any work activities; up and about more than 50% of waking hours
3	Capable of only limited self-care; confined to bed or chair more than 50% of waking hours.
4	Completely disabled; cannot carry on any self-care; totally confined to bed or chair
5	Dead.

\* As published in Am. J. Clin. Oncol.: *Okern, M.M., Creech, R.H., Tormey, D.C., Horton, J., Davis, T.E., McFadden, E.T., Carbone, P.P.: Toxicity And Response Criteria Of The Eastern Cooperative Oncology Group. Am J Clin Oncol 5:649-655, 1982.* The Eastern Cooperative Oncology Group, Robert Comis M.D., Group Chair.

## **12.5 Common Terminology Criteria for Adverse Events V4.0 (CTCAE)**

The descriptions and grading scales found in the revised NCI Common Terminology Criteria for Adverse Events (CTCAE) version 4.0 will be utilized for adverse event reporting. (<http://ctep.cancer.gov/reporting/ctc.html>)

## 12.6 Multiple Myeloma Diagnostic Criteria

Durie, Seminars in Oncology, Vol 13, No 3 (September), 1986:pp300-309:

**Table 1. Diagnostic Criteria**

---

1. Criteria for Diagnosis of Multiple Myeloma

Major criteria

- I. Plasmacytoma on tissue biopsy.
- II. Bone marrow plasmacytosis with >30% plasma cells.
- III. Monoclonal globulin spike on serum electrophoresis exceeding 3.5 g/dL for IgG peaks or 2.0 g for IgA peaks,  $\geq 1.0$  g/24 h of  $\kappa$  or  $\lambda$  light chain excretion on urine electrophoresis in the absence of amyloidosis.

Minor criteria

- a. Bone marrow plasmacytosis with 10% to 30% plasma cells.
- b. Monoclonal globulin spike present, but less than the levels defined above.
- c. Lytic bone lesions.
- d. Normal IgM <50 mg, IgA <100 mg, or IgG <600 mg/dL.

Diagnosis will be confirmed when any of the following features are documented in symptomatic patients with clearly progressive disease. The diagnosis of myeloma requires a minimum of one major + one minor criterion or three minor criteria that must include a + b

1. I + b, I + c, I + d (I + a not sufficient)
2. II + b, II + c, II + d.
3. III + a, III + c, III + d.
4. a + b + c, a + b + d.

## 12.7 Disease Response Criteria

### 12.7.1 MDS Disease Response Criteria

Cheson et al. Clinical application and proposal for modification of the International Working Group (IWG) response criteria in myelodysplasia. *Blood*. 2006; 108:419-425.

Criteria for MDS disease assessment:

Table 3. Proposed modified International Working Group response criteria for altering natural history of MDS

Category	Response criteria (responses must last at least 4 wk)
Complete remission	Bone marrow: < 5% myeloblasts with normal maturation of all cell lines* Persistent dysplasia will be noted† Peripheral blood‡ Hgb > 11 g/dL Platelets > 100 x 10  /L Neutrophils > 1.0 x 10  /L† Blasts 0%
Partial remission	All CR criteria if abnormal before treatment except: Bone marrow blasts decreased by > 50% over pretreatment but still > 5% Cellularity and morphology not relevant
Marrow CR†	Bone marrow: < 5% myeloblasts and decrease by > 50% over pretreatment† Peripheral blood: if HI responses, they will be noted in addition to marrow CR†
Stable disease	Failure to achieve at least PR, but no evidence of progression for > 8 wks
Failure	Death during treatment or disease progression characterized by worsening of cytopenias, increase in percentage of bone marrow blasts, or progression to a more advanced MDS FAB subtype than pretreatment
Relapse after CR or PR	At least 1 of the following: Return to pretreatment bone marrow blast percentage Decrement of > 50% from maximum remission/response levels in granulocytes or platelets Reduction in Hgb concentration by > 1.5 g/dL or transfusion dependence
Cytogenetic response	Complete Disappearance of the chromosomal abnormality without appearance of new ones Partial At least 50% reduction of the chromosomal abnormality
Disease progression	For patients with: Less than 5% blasts: > 50% increase in blasts to > 5% blasts 5%-10% blasts: > 50% increase to > 10% blasts 10%-20% blasts: > 50% increase to > 20% blasts 20%-30% blasts: > 50% increase to > 30% blasts Any of the following: At least 50% decrement from maximum remission/response in granulocytes or platelets Reduction in Hgb by > 2 g/dL Transfusion dependence
Survival	Endpoints: Overall: death from any cause Event free: failure or death from any cause PFS: disease progression or death from MDS DFS: time to relapse Cause-specific death: death related to MDS

Deletions to IWG response criteria are not shown.

To convert hemoglobin from grams per deciliter to grams per liter, multiply grams per deciliter by 10.

MDS indicates myelodysplastic syndromes; Hgb, hemoglobin; CR, complete remission; HI, hematologic improvement; PR, partial remission; FAB, French-American British; AML, acute myeloid leukemia; PFS, progression-free survival; DFS, disease-free survival.

\*Dysplastic changes should consider the normal range of dysplastic changes (modification).

†Modification to IWG response criteria.

‡In some circumstances, protocol therapy may require the initiation of further treatment (eg, consolidation, maintenance) before the 4-week period. Such patients can be included in the response category into which they fit at the time the therapy is started. Transient cytopenias during repeated chemotherapy courses should not be considered a interrupting durability of response, as long as they recover to the improved counts of the previous course.

Criteria for MDS hematologic improvement assessment:

**Table 4. Proposed modified International Working Group response criteria for hematologic improvement?**

Hematologic improvement*	Response criteria (responses must last at least 8 wk)†
Erythroid response (pretreatment, < 11 g/dL)	Hgb increase by $\geq 1.5$ g/dL Relevant reduction of units of RBC transfusions by an absolute number of at least 4 RBC transfusions/8 wk compared with the pretreatment transfusion number in the previous 8 wk. Only RBC transfusions given for a Hgb of $\leq 9.0$ g/dL pretreatment will count in the RBC transfusion response evaluation‡
Platelet response (pretreatment, $< 100 \times 10^9/L$ )	Absolute increase of $\geq 30 \times 10^9/L$ for patients starting with $> 20 \times 10^9/L$ platelets Increase from $< 20 \times 10^9/L$ to $> 20 \times 10^9/L$ and by at least 100%†
Neutrophil response (pretreatment, $< 1.0 \times 10^9/L$ )	At least 100% increase and an absolute increase $> 0.5 \times 10^9/L$ †
Progression or relapse after HI‡	At least 1 of the following: At least 50% decrement from maximum response levels in granulocytes or platelets Reduction in Hgb by $\geq 1.5$ g/dL Transfusion dependence

Deletions to the IWG response criteria are not shown.

To convert hemoglobin levels from grams per deciliter to grams per liter, multiply grams per deciliter by 10.

Hgb indicates hemoglobin; RBC, red blood cell; HI, hematologic improvement.

\*Pretreatment counts averages of at least 2 measurements (not influenced by transfusions)  $\geq 1$  week apart (modification).

†Modification to IWG response criteria.

‡In the absence of another explanation, such as acute infection, repeated courses of chemotherapy (modification), gastrointestinal bleeding, hemolysis, and so forth. It is recommended that the 2 kinds of erythroid and platelet responses be reported overall as well as by the individual response pattern.

## 12.7.2 Multiple Myeloma Disease Response Criteria

Durie et al. International uniform response criteria for multiple myeloma. *Leukemia*. 2006; 20:1467-1473.

Criteria for multiple myeloma disease assessment:

**Table 5** International Myeloma Working Group uniform response criteria: CR and other response categories

Response subcategory	Response criteria a
sCR	CR as defined below plus Normal FLC ratio and Absence of clonal cells in bone marrow b by immunohistochemistry or immunofluorescence c
CR	Negative immunofixation on the serum and urine and Disappearance of any soft tissue plasmacytomas and ≤5% plasma cells in bone marrow b
VGPR	Serum and urine M-protein detectable by immunofixation but not on electrophoresis or 90% or greater reduction in serum M-protein plus urine M-protein level <100 mg per 24 h
PR	≥50% reduction of serum M-protein and reduction in 24-h urinary M-protein by ≥90% or to <200 mg per 24 h If the serum and urine M-protein are unmeasurable, d a ≥50% decrease in the difference between involved and uninvolved FLC levels is required in place of the M-protein criteria If serum and urine M-protein are unmeasurable, and serum free light assay is also unmeasurable, ≥50% reduction in plasma cells is required in place of M-protein, provided baseline bone marrow plasma cell percentage was ≥30% In addition to the above listed criteria, if present at baseline, a ≥50% reduction in the size of soft tissue plasmacytomas is also required
SD (not recommended for use as an indicator of response; stability of disease is best described by providing the time to progression estimates)	Not meeting criteria for CR, VGPR, PR or progressive disease

Abbreviations: CR, complete response; FLC, free light chain; PR, partial response; SD, stable disease; sCR, stringent complete response; VGPR, very good partial response.

aAll response categories require two consecutive assessments made at anytime before the institution of any new therapy; all categories also require no known evidence of progressive or new bone lesions if radiographic studies were performed. Radiographic studies are not required to satisfy these response requirements.

bConfirmation with repeat bone marrow biopsy not needed.

cPresence/absence of clonal cells is based upon the  $k/\lambda$  ratio. An abnormal  $k/\lambda$  ratio by immunohistochemistry and/or immunofluorescence requires a minimum of 100 plasma cells for analysis. An abnormal ratio reflecting presence of an abnormal clone is  $k/\lambda$  of >4:1 or <1:2.

dRefer to Table 4 for definitions of measurable disease.

**Table 6** International Myeloma Working Group uniform response criteria: disease progression and relapse

Relapse subcategory	Relapse criteria
Progressive disease a To be used for calculation of time to progression and progression-free survival end points for all patients including those in CR (includes primary progressive disease and disease progression on or off therapy)	Progressive Disease: requires any one or more of the following:  Increase of $\geq 25\%$ from baseline in Serum M-component and/or (the absolute increase must be $\geq 0.5 \text{ g/dl}$ ) b Urine M-component and/or (the absolute increase must be $\geq 200 \text{ mg/24 h}$ ) Only in patients without measurable serum and urine M-protein levels: the difference between involved and uninvolved FLC levels. The absolute increase must be $> 10 \text{ mg/dl}$ . Bone marrow plasma cell percentage: the absolute % must be $\geq 10\%$ c Definite development of new bone lesions or soft tissue plasmacytomas or definite increase in the size of existing bone lesions or soft tissue plasmacytomas Development of hypercalcemia (corrected serum calcium $> 11.5 \text{ mg/dl}$ or $2.65 \text{ mmol/l}$ ) that can be attributed solely to the plasma cell proliferative disorder
Clinical relapse a	Clinical relapse requires one or more of: Direct indicators of increasing disease and/or end organ dysfunction (CRAB features) b It is not used in calculation of time to progression or progression-free survival but is listed here as something that can be reported optionally or for use in clinical practice 1. Development of new soft tissue plasmacytomas or bone lesions 2. Definite increase in the size of existing plasmacytomas or bone lesions. A definite increase is defined as a 50% (and at least 1 cm) increase as measured serially by the sum of the products of the cross-diameters of the measurable lesion 3. Hypercalcemia ( $> 11.5 \text{ mg/dl}$ [ $2.65 \text{ mmol/l}$ ]) (see Table 3 for further details) 4. Decrease in hemoglobin of $\geq 2 \text{ g/dl}$ [ $1.25 \text{ mmol/l}$ ] (see Table 3 for further details) 5. Rise in serum creatinine by $2 \text{ mg/dl}$ or more [ $177 \mu\text{mol/l}$ or more]
Relapse from CR a (To be used only if the end point studied is DFS) d	Any one or more of the following: Reappearance of serum or urine M-protein by immunofixation or electrophoresis Development of $\geq 5\%$ plasma cells in the bone marrow c Appearance of any other sign of progression (i.e., new plasmacytoma, lytic bone lesion, or hypercalcemia see below)

Abbreviations: CR, complete response; DFS, disease-free survival.

aAll relapse categories require two consecutive assessments made at anytime before classification as relapse or disease progression and/or the institution of any new therapy.

bFor progressive disease, serum M-component increases of  $\geq 1 \text{ gm/dl}$  are sufficient to define relapse if starting M-component is  $\geq 5 \text{ g/dl}$ .

cRelapse from CR has the 5% cutoff versus 10% for other categories of relapse.

dFor purposes of calculating time to progression and progression-free survival, CR patients should also be evaluated using criteria listed above for progressive disease.

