**Multiple Myeloma (Cohort 2, enrollment has been completed and no further enrollment will be allowed)**

11. Be willing and able to provide written informed consent/assent for the trial. The subject may also provide consent/assent for Future Biomedical Research. However, the subject may participate in the main trial without participating in Future Biomedical research.

12. Be  $\geq$  18 years of age on day of signing informed consent.

13. Has a confirmed diagnosis of multiple myeloma based on standard criteria (see Durie 1986 for criteria [84]). See Appendix 12.6 for MM Diagnostic Criteria.

14. Currently has MM with measurable disease, defined as:

- a monoclonal immunoglobulin spike on serum electrophoresis of at least 0.5 g/dL and/or
- urine monoclonal protein levels of at least 200 mg/24 hours
- for subjects without measurable serum and urine M-protein levels, an abnormal free light chain ratio (normal value: 0.26 - 1.65) with involved FLC level  $\geq$  10 mg/dL ( $\geq$  100 mg/L).

15. Has relapse refractory or refractory MM who has failed at least two lines of prior therapy, including a proteasome inhibitor (bortezomib, carfilzomib) and an IMiD (thalidomide, pomalidomide, lenalidomide).

- a. **Relapse Refractory MM** defined as achieving at least a partial response to previous treatment with a proteasome inhibitor or an IMiD, or both, but progressed within 6 months (and had developed progressive disease on or within 60 days after completing their last treatment)
- b. **Refractory MM** defined as progressed on or within 60 days of treatment with a proteasome inhibitor or an IMiD, or both (and had developed progressive disease on or within 60 days after completing their last treatment)

16. Be able to provide archival (if available) and newly obtained bone marrow aspirate/biopsy material for biomarker analysis and disease assessment.

17. Must have a performance status of 0 or 1 on the ECOG Performance Scale.

18. Must demonstrate adequate organ function as defined by the following table (Table 2). All screening laboratory tests should be performed within 7 days of treatment initiation.

Table 2      Multiple Myeloma Adequate Organ Function Laboratory Values

System	Laboratory Value
Hematological	
Absolute neutrophil count (ANC)	$\geq 1,000 / \mu\text{L}$
Platelets	$\geq 75,000 / \mu\text{L}$
Hemoglobin	$\geq 8 \text{ g/dL}$
Renal	

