#### **MM (Cohort 2)**

The primary efficacy endpoint for the MM cohort is ORR, defined as the proportion of subjects in the analysis population who have response according to the IMWG criteria at any time during the study. Response for the primary analysis will be determined by the investigator.

Key secondary efficacy endpoints for the MM cohort include:

- CR + sCR rate based on IMWG criteria (investigator-assessed)
- TTP
- DOR
- PFS
- OS
- PD-L1 expression at baseline among responders/non-responders

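### Cohort 2 (myeloma): a subject measurable only by free light chains can be scored VGPR, and so count as a primary responder, with no change in disease

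*Combined protocol and SAP*

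**What the plan says.** Section 5.1.2, criterion 14, defines measurable disease for Cohort 2 in three ways: a serum spike of at least 0.5 g/dL, urine M-protein of at least 200 mg/24 h, or a third route, "for subjects without measurable serum and urine M-protein levels, an abnormal free light chain ratio" with an involved FLC of at least 10 mg/dL.

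Section 12.7.2 (Table 5) gives the response categories:

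- **PR:** where serum and urine M-protein are unmeasurable, a 50% or greater "decrease in the difference between involved and uninvolved FLC levels is required in place of the M-protein criteria".
- **VGPR:** either "Serum and urine M-protein detectable by immunofixation but not on electrophoresis", or a reduction of 90% or more in serum M-protein with urine M-protein below 100 mg per 24 h. Neither alternative mentions FLC.
- **CR:** "Negative immunofixation on the serum and urine and Disappearance of any soft tissue plasmacytomas and ≤5% plasma cells in bone marrow". FLC is not mentioned.
- **sCR:** "CR as defined below plus Normal FLC ratio" and absence of clonal marrow cells.

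Footnote a requires two consecutive assessments for every category and no known progressive or new bone lesions. Section 8.2.3.1 defines the Cohort 2 primary endpoint as the "proportion of subjects in the analysis population who have response according to the IMWG criteria at any time during the study", judged by the investigator. The title of Table 21 counts PR or better as an overall response. Section 8.2.7 tests ORR against 25% at one-sided 5% and requires 12 of 28 responses.

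**The concern.** The entry criteria and the response table do not fit together for one kind of subject. For someone who enters by the FLC route, FLC is the only measurable parameter, yet the table asks for an FLC change at PR and not at VGPR, the better category. The first VGPR alternative makes no comparison with baseline. A subject whose M-protein shows on immunofixation but not on electrophoresis at screening is already in the VGPR state before the first dose. Remaining there for two visits satisfies the confirmation rule.

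The ordering also breaks down. An FLC-only subject with, say, a 40% fall in the FLC difference fails PR but can be placed in the higher category. Table 6 does give these subjects an FLC criterion for progression, so the gap is confined to the upper response categories.

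At stake is the primary test. Any such subject is a response that owes nothing to treatment, and ORR counts it permanently because response at any time suffices.

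**Working it through.** **Step 1: follow one subject through the text.** Take a subject admitted by the FLC route, immunofixation positive and electrophoresis negative in serum and urine, with no change on treatment.

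| Row or rule | Requirement | Met if unchanged? |
|---|---|---|
| PR | FLC difference down by at least 50% | No |
| VGPR, first alternative | immunofixation positive, electrophoresis negative | Yes |
| VGPR, second alternative | serum M-protein down by at least 90%, with urine below 100 mg/24 h | No |
| Footnote a | two consecutive assessments, no progressive or new bone lesions | Yes |
| SD | not CR, VGPR, PR or progression | No, because VGPR is met |

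The SD row lists CR, VGPR and PR as separate alternatives. No section makes VGPR conditional on PR. The subject is a confirmed VGPR and counts toward ORR.

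**Step 2: reproduce the plan's rule.** Inputs from Section 8.2.7: n = 28, null rate 0.25, alternative 0.50, success at 12 or more.

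- P(Bin(28, 0.25) ≥ 12) = 0.0294
- P(Bin(28, 0.25) ≥ 11) = 0.0679, so 12 is the smallest threshold that keeps the error below 5%
- P(Bin(28, 0.50) ≥ 12) = 0.8275, against a stated power of about 80%

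The threshold is reproduced. The exact power is slightly above the rounded figure, and nothing here depends on it.

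**Step 3: add k automatic responders.** The documents do not give k, so it is an assumption shown over a range. The other 28 − k subjects are taken to respond at 25%. Success then needs 12 − k responses among them:

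error(k) = P(Bin(28 − k, 0.25) ≥ 12 − k)

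expected ORR(k) = [k + 0.25 × (28 − k)] / 28

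| k | Calculation | One-sided error | Expected ORR |
|---|---|---|---|
| 0 | P(Bin(28, 0.25) ≥ 12) | 0.0294 | 25.0% |
| 1 | P(Bin(27, 0.25) ≥ 11) | 0.0528 | 27.7% |
| 2 | P(Bin(26, 0.25) ≥ 10) | 0.0909 | 30.4% |
| 3 | P(Bin(25, 0.25) ≥ 9) | 0.1494 | 33.0% |

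**Step 4: vary the assumption about the rest.** If the other subjects respond at 10% instead of 25%, the chance of success at k = 3 is only 0.0005. The inflation matters near the null boundary, and a handful of automatic responders would not carry a nearly inactive drug to success.

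**The case against.** Four objections deserve weight.

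1. **The table is an excerpt.** Sections 3.1 and 7.1.2.7.1 make the published IMWG 2006 criteria the standard. Section 12.7.2 reproduces only part of them: footnote d points to a Table 4 on measurable disease, and the only response-criteria Table 4 in the document is the MDS one. The full source might nest VGPR within PR. That cannot be checked here. It does not remove the point, because this protocol pairs the excerpt with its own FLC entry route and leaves the link unstated.

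2. **Few subjects are exposed.** A reader might infer that every FLC-only subject scores automatically. The documents do not support that. A subject with a visible spike below 0.5 g/dL fails the electrophoresis part, and one with negative immunofixation fails the other part. Read strictly, the row asks for positivity in both serum and urine. This stands: the exposed group is a subset of the FLC-only subjects.

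3. **CR is different.** A reader might infer that unchanged subjects would equally be scored CR, since that row also has no FLC term. CR, however, also needs 5% or fewer marrow plasma cells and no plasmacytomas. Criterion 15 requires recent progression. For a subject without a spike, every qualifying combination in Section 12.6 includes a plasmacytoma or more than 30% marrow plasma cells, although that diagnosis may be historical. An unchanged CR is possible on paper but unlikely. This also stands.

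4. **Investigators would notice.** Response is investigator-assessed and FLC is a listed response parameter in Flow Charts B and D. Many investigators would not record VGPR with FLC unchanged. That is plausible, but it relies on judgement overriding the written rule.

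**Conclusion.** The point holds for the first VGPR alternative. As written, an FLC-only subject who is immunofixation positive and electrophoresis negative at baseline can be a confirmed VGPR, and hence a primary responder, with no change in disease. The CR row shares the omission, but there it has little practical force.

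It would go too far to say that the Cohort 2 error rate is above 5%. That is conditional on k, which the documents do not give. With none of these subjects the error is 0.029 and the design is intact. With one it is 0.053, just over the limit. The larger figures need two or three among 28. All of them assume that the remaining subjects respond at 25%.

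It would also go too far to say that the documents imply a 90% FLC fall for VGPR or a normal FLC ratio for CR. The table attaches neither to those categories, and imposing them would alter the cited IMWG 2006 endpoint.

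**What to change.** State in Section 12.7.2 and in Section 8.2.3.1 (Cohort 2) that a subject whose only measurable disease at baseline is serum FLC counts toward ORR, or toward CR + sCR, only if the PR row's FLC requirement is also met, that is, a fall of at least 50% in the difference between involved and uninvolved FLC. This uses a threshold already in the table and sets no new one for VGPR or CR.

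Re-derive both rates from the FLC values already collected; Flow Charts B and D schedule the assay at screening and at the on-treatment myeloma assessments. In the CSR, report the number of FLC-only subjects and give ORR and CR + sCR with and without the rule. If no subject is affected, that report settles the matter.

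The cost is a short text addition and a re-derivation, with no new data. ORR can only stay the same or fall slightly. Cohort 2 has finished enrolment and treatment, so the rule comes after the fact in an open-label cohort and must be reported as a change. Section 8.1 already allows Cohort 2 analyses to be modified, with changes described in the CSR.
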